6.7.5.3. Number and Proportion of Days with Angioedema Symptoms

The number of days with angioedema symptoms is the sum of the days during the entire dosing period prior to discontinuation of treatment for which at least 1 symptom is reported during an expert-confirmed HAE event.

This endpoint will be determined for Parts 1 and 2 as expert-confirmation will not be calculated for Part 3. As with the calculation of event rate, if the subject discontinues treatment during the reporting period, any symptoms during confirmed attacks that occur within 24 hours after last dose will be counted in the calculation of days with angioedema symptoms and the additional 24-hour period will be included in the duration of the reporting period.

The percentage of days with angioedema symptoms is derived as the number of days with angioedema symptoms divided by the duration of the treatment period of interest.

6.7.5.4. Responder Endpoint

A subject is defined as being a responder to study treatment if the rate of adjusted confirmed events during study treatment represents at least a 50% relative reduction compared with the baseline event rate as defined in Section 6.6.1.

The relative reduction is calculated for Part 1 as:

$$\begin{aligned} & \text{Relative reduction} \\ &= \frac{\text{Baseline event rate} - \text{Adjusted confirmed event rate on treatment}}{\text{Baseline event rate}} \times 100\% \end{aligned}$$

where the adjusted confirmed event rate while on study treatment is computed as shown in Section 6.7.5.1.

A subject is classified as a responder if the relative reduction in monthly event rate for Part 1 is $\geq 50\%$. Otherwise, the subject is classified as a non-responder.

Responder analysis will be conducted for Part 1 only. Additional responder analyses will be conducted for 70% and 90% relative reduction, defined similarly.

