6.7.5. Derived Efficacy Endpoints

6.7.5.1. Event Rate

General Formula for Event Rate

In general, the formula for computing an event rate is the number of events meeting the event criteria divided by the duration of treatment during the reporting period of interest. Duration of treatment during the reporting period of interest = the last day in the reporting period – first day in the reporting period + 1.

$$\begin{aligned} \text{Event Rate} \left(\frac{\text{events}}{\text{month}} \right) \text{ During Reporting Period of Interest} \\ = \frac{\text{Number of Events} * 28}{\text{Duration of Treatment During Reporting Period in Days}} \end{aligned}$$

If the subject discontinues treatment early, any events that occur within 24 hours after last dose will be counted in the calculation of event rate and the additional 24-hour period will be included in the duration of the reporting period.

Subject-Reported Event Rate

Diary entries for events and investigator-collected events that are not captured in the diary are considered subject-reported events. The expert reviews each event and either confirms it as an event or rejects it as an event. For Part 3, there is no expert review of attacks, but an adjusted subject-reported attack rate will be computed based on a list of programmable requirements.

Subject-reported event rates will be computed for the entire dosing period only (ie, not for the effective dosing period or by month) for Parts 1, 2, and 3.

Adjusted Subject-Reported Attack Rate for Part 3

Because there is no expert-confirmation of attacks during Part 3, an adjusted subject-reported attack rate will be computed.

Subject-reported attacks must meet the following criteria (applied in order) for inclusion in the adjusted subject-reported rate computation:

- Attack must include at least 1 symptom of swelling
- Subject response to diary question, “In retrospect, could there be an alternative explanation for your symptoms other than an HAE attack (ie, allergic reaction, viral cold, etc)?” must be “no”

- Attack must be unique (attack begins > 24 hours from end of the prior attack), otherwise the event will be combined with and treated as a continuation of the preceding attack
- If untreated, attack must have a duration > 24 hours

Adjusted subject-reported attack rates will be computed for the following reporting periods and expressed in units of attacks/month where 1 month = 28 days:

- Part 3, by month
- Part 3, entire dosing period

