For adjusted subject-reported attack rates by month, months will be defined in blocks of 28 days, beginning on the first day of dosing in Part 3. If the subject discontinues treatment early, any attacks that occur within 24 hours after last dose will be counted in the calculation of subject-reported adjusted attack rate and the additional 24 hour-period will be included in the duration of the reporting period.

Confirmed Event Rate

Confirmed event rates will be computed based on the number of expert-confirmed events that occur during the reporting period of interest.

Confirmed event rates will be computed for the following reporting periods and expressed in units of events/month where 1 month = 28 days:

- Parts 1 and 2, by month
- Parts 1 and 2, entire dosing period
- Parts 1 and 2, effective dosing period

Confirmed event rates will be computed for Part 1 and at the end of Part 2. For confirmed event rates by month, months will be defined in blocks of 28 days, beginning on Day 1, the day of first dose. The entire dosing period begins on Day 1 or adjusted Day 1 during Part 2 for subjects originally randomized to placebo. The effective dosing period similarly begins on Day 8 or adjusted Day 8. Part 1 continues until the time of Part 2 dose. Part 2 continues until the time of the first dose for Part 3. Expert confirmation is not done in Part 3 and so confirmed event rate will not be computed for Part 3. If the subject discontinues treatment early, the reporting period will continue through 24 hours post last dose and any events that occur within 24 hours after last dose will be counted in the calculation of events rate. If there are confirmed events in the eCRF without corresponding diary information, as may happen if a subject verbally reports an event to an investigator but does not enter it into the e-diary, the event will be counted.

For sensitivity analyses for missing data for the Part 1 primary analysis, confirmed event rates for the entire dosing period for subjects who discontinue treatment early will be re-computed as a weighted average of the observed post-treatment discontinuation event rate and an imputed event rate for periods of missing data post-treatment discontinuation. Details are provided in Section 6.8.1.

Expert-Confirmed Event Rate by Location

Expert-confirmed abdominal-only, peripheral, and mixed event rates will be computed using the location definitions provided in Section 6.7.5.9.

Adjusted Expert-Confirmed Event Rate

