An adjusted expert-confirmed event rate will be computed for use in the determination of the 50%, 70%, and 90% responder endpoints comparing post-baseline event rates to baseline event rates. For the adjusted expert-confirmed event rate, the 2 additional requirements for confirmation of event rates used during screening will be applied to post-baseline expert-confirmed events to determine the number of confirmed events meeting the additional requirements. The additional requirements are:

- The events are unique, which is defined as an event that does not begin within 48 hours of the end of a previous event.
- The events must have either been treated, required medical attention or be documented to cause functional impairment based on subject entry in the diary. Functional impairment is defined as the subject being unable to perform their daily activities without restriction (ie, subject records that they are at least slightly restricted in their daily activities during their HAE event).

6.7.5.2. Number and Percentage of Subjects Who Are Event Free Over Entire Dosing Period and Effective Dosing Period

The following event-free endpoints will be derived for the entire dosing period and for the effective dosing period for Parts 1 and 2:

- The number and percentage of subjects with no confirmed events during the period of interest. Subjects with no confirmed events who discontinue before the end of the planned treatment period are not considered event-free.

The event-free rate for active treatment for subjects originally randomized to placebo will be based on the initial 24-week period during Part 2.

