8.8. Analysis of Additional Exploratory Efficacy Endpoints

8.8.1. Number and Proportion of Subjects with No Events

The number and proportion of subjects with no events over 24 weeks is an exploratory endpoint for Part 1. This information will be descriptively summarized. The summary will be repeated at the end of Part 2 as a summary of the number and proportion of subjects with no events over the entire dosing period of 52 weeks for those originally randomized to active treatment. A summary of 24-Week data at the end of Part 2 will be conducted including subjects originally randomized to placebo. The summary will show the number and proportion of subjects with no events during the first 24 weeks of active treatment, whether received in Part 1 or Part 2 and separately for those who started active treatment in Part 2. Subjects who discontinue treatment prior to the end of the reporting period of interest will not be considered event-free. A separate summary of the number and proportion of subjects with no adjusted subject-reported events in Part 3 will be provided.

For Part 1, a chi-squared test will be used to test whether there is a difference in the proportion of subjects with no events comparing each active dose to placebo. For the chi-squared analysis, if the expected number of subjects in any individual cell is < 5 , Fisher's exact test will be used instead the chi-squared test.

A KM plot and corresponding summary of time to first event will be produced for Part 1 for both the entire dosing period and the effective dosing period (Day 8 to Week 24).

8.8.2. Proportion of Responders to Study Drug.

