Subjects will be classified as responders or non-responders for Part 1 as discussed in Section 6.7.5.4. A responder is defined as a subject who has at least a 50% relative reduction in the rate of expert-confirmed HAE events meeting the stricter screening criteria during treatment compared with the baseline event rate. A summary of the number and proportion of responders by study treatment will be produced. Logistic regression with responder status as the outcome variable and treatment and baseline event rate as independent variables in the model will be used to compare each active treatment to placebo treatment. Point estimates of the odds ratios for response comparing 110 mg to placebo and 150 mg to placebo will be calculated along with corresponding 95% CIs. If the proportion of responders is near zero for the placebo treatment (or for either active treatment), logistic regression may not be an appropriate methodology for analysis and Fisher's exact test will be used in place of logistic regression. This analysis will also be conducted for responders with at least 70% and 90% relative reduction and conducted by subgroups for 50%, 70%, and 90% relative reduction. Forest plots will be produced to accompany the subgroup analyses.

A waterfall plot of relative reduction by treatment will be produced. For the combined study, this plot will include differentiation in the bar fill for Japan and the rest of the world.

A listing of expert-confirmed events that are not included in any adjusted expert-confirmed events will be provided.

The relationship of selected baseline characteristics with the proportion of responders with at least 50% and 70% relative reduction, respectively, will be explored using an appropriate model-building method for Part 1.

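### Responder status has no rule for early discontinuers: a subject who stops within days without a qualifying event is a 100% responder, yet is refused event-free status

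*SAP*

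**What the plan says.** **Responder endpoint.** SAP 6.7.5.4 compares the baseline event rate with the adjusted confirmed rate, "where the adjusted confirmed event rate while on study treatment is computed as shown in Section 6.7.5.1". The classification reads "A subject is classified as a responder if the relative reduction in monthly event rate for Part 1 is" at least 50%. For the other two thresholds, "Additional responder analyses will be conducted for 70% and 90% relative reduction, defined similarly". SAP 8.8.2 repeats the definition for events "meeting the stricter screening criteria during treatment compared with the baseline event rate" and adds no condition about completing treatment.

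**The rate.** SAP 6.7.5.1 divides events by duration of treatment. It says "If the subject discontinues treatment early, any events that occur within 24 hours after last dose will be counted in the calculation of event rate", with that extra day added to the denominator. For confirmed rates it says "If the subject discontinues treatment early, the reporting period will continue through 24 hours post last dose". No minimum exposure is set.

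**Event-free endpoint.** SAP 6.7.5.2 says "Subjects with no confirmed events who discontinue before the end of the planned treatment period are not considered event-free". SAP 8.8.1 repeats it: "Subjects who discontinue treatment prior to the end of the reporting period of interest will not be considered event-free".

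**Missing data.** The two analyses in SAP 6.8.1 and 8.6.2 that use or impute data after stopping treatment are tied to the primary event rate. They are not applied to responder status.

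**Status.** Protocol 7.1.3 and SAP 3.2.3 list both binary endpoints as exploratory. Both describe the responder rate as the rate during treatment.

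**The concern.** A rate over a very short exposure says little about response, yet zero events over any exposure gives the largest possible reduction. The SAP deals with this problem for one binary endpoint and leaves it open for the other. One subject can therefore be a 90% responder in one table and not event-free in the next.

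The subjects affected may be those for whom treatment failed. SAP Table 14 treats stopping for an adverse event or perceived lack of efficacy as not missing at random and gives such subjects an unfavourable imputed rate, but only in a sensitivity analysis of the primary endpoint. For responder status the same subjects can count as full successes.

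The responder result is more than a listing. SAP 8.8.2 compares each dose with placebo by logistic regression or Fisher's exact test, repeats this by subgroup with forest plots, and models responder status on baseline characteristics. The combined output with Study 302 carries it too.

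A related gap: SAP 6.5.2 keeps randomized but undosed subjects in the ITT population. They have no on-treatment rate, so their responder status is undefined.

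**Working it through.** The plan states no responder figure for this study, so there is none to reproduce. The check applies the SAP formulas and then illustrates the size.

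**Inputs**
- Mean baseline rate in Study 302: 2.98 per month (Protocol 5.3.1).
- Minimum qualifying baseline: 2 events in 56 days (Protocol 8.2.1), so 2 × 28/56 = 1.0 per 28 days.
- Planned arm size: 8 (SAP 4.1).
- Subjects completing 24 weeks of dosing in Study 302 (Protocol 5.3.1): 37 of 40 (150 mg), 37 of 41 (110 mg), 34 of 39 (placebo).
- Full Part 1 period: 169 days (the denominator in SAP 6.8.1).
- Assumed, not in the documents: events follow a Poisson process, the drug has no effect, and last dose falls on Day 7 or Day 14. With the added 24 hours, 8 or 15 days are counted.

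**1. The rule applied**

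Rate = events × 28 / days counted. Reduction = (baseline − rate) / baseline × 100%. With no qualifying events the rate is 0 and the reduction is 100%, whatever the baseline or exposure. The subject passes 50%, 70% and 90%, but is not event-free under SAP 6.7.5.2.

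**2. Chance of no event without any drug effect**

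P = exp(−rate × days / 28).
- Baseline 2.98, last dose Day 7: exp(−2.98 × 8/28) = 0.43.
- Baseline 2.98, last dose Day 14: exp(−2.98 × 15/28) = 0.20.
- Baseline 1.0, last dose Day 7: exp(−1.0 × 8/28) = 0.75.

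**3. The same untreated subject followed for the full period**
- Baseline 1.0: expected events 169/28 = 6.04. The 50% threshold allows at most 3 events, with probability 0.15. The 70% threshold allows at most 1 (0.017), and the 90% threshold none (0.002).
- Baseline 2.98: expected events 2.98 × 169/28 = 17.99. The 50% threshold allows at most 8, with probability 0.007.

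**4. The opposite error**

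Take baseline 2.98 and a true 60% reduction, so a rate of 0.4 × 2.98 = 1.19. With last dose on Day 7, the chance of at least one event is 1 − exp(−1.19 × 8/28) = 0.29. One event gives 28/8 = 3.5 per month, a reduction of (2.98 − 3.5)/2.98 = −17%. That true responder fails the 50% threshold and so all three.

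**5. How much one subject matters, and how often it could arise**
- One subject in an arm of 8 is 1/8 = 12.5 percentage points.
- Study 302 non-completion: 3/40 = 7.5%, 4/41 = 9.8%, 5/39 = 12.8%. (The protocol prints 85% completion for placebo; 34/39 is 87%.)
- If those rates applied here, the chance of at least one discontinuer in an arm of 8 is 1 − (37/40)^8 = 46%, 1 − (37/41)^8 = 56% and 1 − (34/39)^8 = 67%.
- The timing of stopping is not given, so the frequency of early stops without an event cannot be estimated.

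**The case against.** **No rule is breached.** A reader might infer that the responder definition violates the SAP's own rule. It does not. The discontinuer rule is written only for event-free status, an absolute state over 24 weeks that needs the whole period. The responder endpoint is a rate scaled for duration, both documents define it during treatment, and it follows the on-treatment estimand in SAP 8.6.1. This stands: the point is an inconsistency between two definitions, for which the SAP gives no reason.

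**A per-protocol version is planned.** Table 14.2.6.1.2 (and 14.2.6.1.2.C for the combined study) repeats the responder display in the per-protocol population, which is limited to Part 1 completers. This helps less than it seems. SAP 7.1 defines completion as having a Week 24 visit, and Protocol 8.3.2 asks subjects who stop the drug to keep attending through Week 24. The 85% compliance condition does not reliably remove them either, because SAP 10.2 counts expected capsules only to the last dose. An early discontinuer can remain in that table, and one who is excluded is dropped rather than counted as a failure.

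**The remedy is one choice among several.** Counting every discontinuer as a non-responder also fails subjects who stop for reasons that Table 14 treats as missing at random, such as ineligibility found later. It sets aside diary data that discontinuers are asked to keep recording. This is fair, and is why other versions belong beside it as sensitivity analyses.

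**Conclusion.** The gap is real and minor. As written, SAP 6.7.5.4 and 8.8.2 make any early discontinuer without a qualifying event a responder at all three thresholds. With last dose on Day 7 and no drug effect, the chance is about 43% at a baseline of 2.98 and 75% at 1.0. With last dose on Day 14 and a baseline of 2.98 it is about 20%. These figures rest on the Poisson model and the assumed stopping days.

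A reader might go further and infer that the rule inflates the responder proportions or favours the drug. The documents do not support that. A single event in a short exposure can turn a true responder into a non-responder. Study 302 non-completion was highest on placebo, so counting discontinuers as failures could even widen the drug-placebo difference. The direction of any between-arm bias is not known.

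The endpoint is outside the four-endpoint testing hierarchy in SAP 8.5, so the primary and secondary conclusions are unaffected.

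**What to change.** In SAP 6.7.5.4 and 8.8.2, state that subjects who discontinue study treatment before the end of Part 1, and randomized subjects who were never dosed, are non-responders at 50%, 70% and 90%, in line with SAP 6.7.5.2. Keep the on-treatment version as a sensitivity analysis. Optionally add a version using the rate with post-discontinuation diary data from SAP 6.8.1.

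The cost is one sentence and a repeated table. Responder proportions may be slightly lower, and subjects who stop for reasons unrelated to treatment will also count as non-responders.

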6.7.5.5. Event Duration

The duration of each confirmed on-treatment event will be calculated in hours, based on the start and stop date and time of the confirmed event (time the event finished). Experts have the option to count more than one subject-reported event as a single confirmed event. For a confirmed event that includes more than 1 subject-reported event, the duration is calculated from the start of the first subject-reported event to the end of the last subject-reported event that has been combined into 1 event. A similar adjustment for duration will be made for adjusted subject-reported attacks that are combinations of two or more subject-reported attacks in Part 3. The duration of the event from start of the event to time that the worst was over will also be calculated and summarized.

6.7.5.6. Event Onset Relative to Prior Dose of Study Drug

For each confirmed on-treatment event, the time to event onset from the time of the prior dose of study drug reported in the subject CRF page will be calculated. If there is no dosing time reported for the dose taken prior to the event, the event onset time relative to prior dose will be missing. The event onset time relative to prior dose of study drug information is used in the listing of event data only.

6.7.5.7. Medications to Treat HAE Events

The following medications reported taken as acute treatment in the subject diary will be classified in the analyses as targeted medications to treat subject-reported HAE events: Berinert, Cinryze, Kalbitor, Firazyr, Ruconest, and fresh frozen plasma. Of these, Berinert and Firazyr are approved for use in Japan. Other medications listed in the diary for treatment of HAE events will be considered non-targeted medications to treat subject-reported HAE events.

6.7.5.8. Event Symptoms

Symptoms reported for confirmed on-treatment events will be included in summaries of event characteristics. In addition, listings of diary data will show symptoms for all events, whether subject-reported or expert-confirmed.

6.7.5.9. Event Location

The location of each subject-reported and confirmed event will be determined based on the symptoms indicated in the e-diary as shown in [Table 11](#).

Table 11: Determination of Event Location Using Symptoms Collected in the e-Diary

Abdominal-only event	Mixed Event	Peripheral event (inclusive of skin and airway swelling)
Symptoms checked must only come from this box: 
 • Internal Swelling or Symptoms of Internal Swelling in the Abdomen: 
 • Nausea • Abdominal Discomfort • Cramps (colicky pain) • Vomiting • Abdominal pain • Diarrhea^a 	Must have at least 1 symptom from left and right box (from abdominal and peripheral event characterization)	Symptoms checked must only come from this box: 
 • Visible Swelling: 
 • face/head • neck (outer swelling) • legs, buttocks/genitals • eyes • arms • feet • stomach (outside) • mouth/tongue/lips • hands • chest/back • joints • Internal Swelling or Symptoms of Internal Swelling in the Airways: 
 • lump in throat/tightness • change in voice • difficulty swallowing • difficulty breathing • Pink rings (erythema marginatum)^a

Note: headache and fatigue symptoms may be checked but play no role in characterization of a subject-reported or confirmed event

^a Diarrhea, erythema marginatum, headache, and/or fatigue cannot be selected alone or in combination without another symptom(s) of swelling or internal swelling to be considered a confirmed event.

